5.1 Inclusion Criteria

- a. Age 25 to 90 years.
- b. NSTEMI with troponin I \geq 5.0 ng/dL, with compatible symptoms and ECG changes.
- c. Permission of attending physician.
- d. Ability to understand the risk, benefits, and alternatives of participation.

5.2 Exclusion Criteria

- a. STEMI
- b. Patients requiring invasive support because of compromised hemodynamics.
- c. Scheduled for cardiac surgery.
- d. Current or prior treatment with a PCSK9 antibody.
- e. Current participation in an intervention clinical trial.
- g. Female of childbearing potential. This is a female subject who has not used acceptable method(s) of birth control (see below) for at least one month prior to screening, unless the subject is sterilized or postmenopausal. Menopause is defined as: 12 months of spontaneous and continuous amenorrhea in a female \geq 55 year of age.
 - Acceptable method(s) of birth control definition: One highly effective method (methods that can achieve a failure rate of less than 1% per year when used consistently and correctly)
 - Combined hormonal (estrogen and progestogen) contraception associated with inhibition of ovulation (oral, intravaginal, transdermal)
 - Progestogen-only hormonal contraception associated with inhibition of ovulation (oral, injectable, implantable)
 - Intrauterine device (IUD)
 - Intrauterine hormone-releasing system (IUS)
 - Bilateral tubal occlusion
 - Vasectomized partner
 - Sexual abstinence
 - h. Contraindication to statin therapy.
 - i. Subject likely not to be available to complete all protocol-related study visits or procedures.
 - j. Latex allergy
 - k. History of severe hypersensitivity to any monoclonal antibody.

6. Drugs/ Substances/ Devices

- a. The rationale for choosing the drug and dose or for choosing the device to be used.

The drug evolocumab was chosen because of studies indicating that it reduces inflammation and improves lipid profile in patients already on statin therapy. [12] The dose was chosen based on

that approved by the FDA for clinical use in patients with stable coronary disease, available in the United States and reduces LDL cholesterol. [44]

- b. Justification and safety information if FDA approved drugs will be administered for non-FDA approved indications or if doses or routes of administration or participant populations are changed.

Evolocumab is an FDA approved medication that will be administered for a non-FDA approved indication, hospitalized patients with NSTEMI. This is justified based on clinical and pre-clinical data indicating that vascular and myocardial inflammation is increased in NSTEMI patients, that inflammation is associated with adverse outcomes in this patient group, that in stable CAD patients, anti-inflammatory interventions improve outcomes, and that evolocumab has anti-inflammatory properties. The dose and route of administration are the same as that administered for FDA approved indications.

We are applying for an exemption from the FDA such that an IND is not needed for the proposed mechanistic study in NSTEMI patients. Safety information on the use of these drugs is detailed above.

An IND exemption request will be submitted to the FDA.

7. Study Statistics

- a. Primary outcome variable.

The primary outcome will assess the difference of LDL-C serum concentration between the placebo and evolocumab groups at 30 days. To assess the primary endpoint of the mean percent change from baseline in LDL-C at day 30, a repeated measures linear effects model will be used in comparing the efficacy of evolocumab vs placebo.

- b. Secondary outcome variables.

For the secondary outcome of comparing the changes in target to background ratio (TBR) over time (30-day FDG PET scan minus early hospitalization or shortly following discharge FDG PET scan) between the groups, the following statistical approach will be used consistent with the prior literature.[45] Specifically, difference in the percent change in TBR at 30 days from early hospitalization (30 day – early hospitalization TBR) between the two randomized groups will be compared with ANCOVA using the baseline TBR as a covariate. The percent difference between the index vessel MDS TBR in the placebo and evolocumab groups at 30 days will be analyzed using Kruskal Walis testing.

The non-parametric biomarkers of the secondary endpoint will be log transformed, and the results interpreted as the difference in geometric means between the groups. The analysis will be performed in the primary evaluable population, defined as data from subjects that provided imaging/laboratory data at the indicated time points.

A one-sided p-value ≤ 0.05 will be considered significant, based on the assumption that evolocumab will reduce, and not increase, inflammation.

A one-sided p-value ≤ 0.05 will be considered significant, based on the assumption that evolocumab will reduce, and not increase, inflammation.

- c. Statistical plan including sample size justification and interim data analysis.

We are providing power calculations for the primary as well as key secondary endpoints (see Tables 1-4).

Primary endpoint:

For calculation of power for the primary endpoint, we anticipate median baseline presentation LDL-C of 110 (90 – 130) mg/dL in our patient population. This number is informed by prior ACS trials (i.e. TIMI-22) as well as local experience with the ACS population at the Johns Hopkins Hospital (with approximately 25%-35% of the population already on baseline statin therapy). We expect this LDL-C value to be reduced by approximately 50% by high intensity statin therapy in the standard treatment arm (i.e. LDL-C of 55 (40- 70) mg/dL at 30 days). We anticipate a further 50% lowering of LDL-C at 30 days after the administration of evolocumab (i.e. LDL-C of 28 (14 – 42) mg/dL. As is shown below (Table 1), using a one-sided p-value of 0.05, the study has nearly 100% power to detect this difference, and will have 80% power to detect an absolute LDL-C reduction of 9.5 mg/dL (17% reduction in LDL-C at 30 days). Additionally, Table 2 presents the expected mean \pm SD baseline and 30-day LDL-C levels and the expected percent LDL-C change in the placebo and evolocumab arms.

Table 1

N in each group	Median (IQR) LDL-C in ACS Population at baseline	Anticipated Percent LDL-C Reduction in the Standard of Care Arm	Estimated Power to Detect a 50% Additional LDL Lowering	Detectable Point Estimate at 80% Power
N = 30	110 (90-130)	50% (40 – 60%)	99+%	-9.5 mg/dL

Table 2: Expected mean \pm SD LDL-C levels at baseline and thirty days and the percent change from baseline to 30 days in the placebo and evolocumab groups.

Groups:		LDL-C, mg/dl		% change from baseline, mean (SD)
		Baseline, mean (SD)	30 day, mean (SD)	
Atorvastatin 80mg	+Placebo	110 (\pm 14)	55 (\pm 11)	-50 (\pm 12)
	+Evolocumab		28 (\pm 10)	-75 (\pm 14)

Secondary Endpoint:

Previously published clinically relevant, drug-induced TBR changes are reported in the range of 5%-15%. [46] The power calculations for a 10% and 15% TBR difference based on a sample size of 30 patients per study arm are outlined in Table 3 & 4 below. The primary outcome for this calculation of sample is the % difference in TBR between the groups at 30 days in the most diseased segment of aorta or carotid artery. Table 1 uses a 1-sided p-value of 0.05, under the hypothesis that evolocumab will lower inflammation and will not raise it, consistent with the approach used in the Dal-PLAQUE study. For completeness, we replicated the analysis in Table 4 using a 2-sided p-value of 0.05. Calculations are performed using non-parametric statistics accounting for the possibility of non-normally distributed TBR data; calculations using parametric statistics and the following anticipated means and standard deviations yield similar results, as shown in Table 5 below:

Table 3: Power calculations using a 1-sided p-value, i.e. only assumes that PCSK9 inhibition will lower TBR in the most diseased segment (MDS) and will not raise TBR.

		Estimated Power	Detectable
--	--	-----------------	------------

	N in each group	Median (IQR) TBR in ACS Population at 30 days	at 10% & 15% TBR Difference	Point Estimate at 70% & 80% Power
Aorta MDS	N = 30	3.2 (2.7 – 4.0)	66% 93%	-10.6% -12.0%
Carotid MDS	N = 30	2.5 (2.1 – 3.0)	78% 98%	-9.0% -10.2%

Table 4: Power calculations using a standard 2-sided p-value of 0.05

	N in each group	Median (IQR) TBR in ACS Population at 30 days	Estimated Power at 10% & 15% TBR Difference	Detectable Point Estimate at 70% & 80% Power
Aorta MDS	N = 30	3.2 (2.7 – 4.0)	54% 87%	-12.0% -13.6%
Carotid MDS	N = 30	2.5 (2.1 – 3.0)	68% 95%	-10.4% -11.6%

The tables above show fair to good power to demonstrate a difference of 10%, and an excellent power to show a difference of 15% in the primary outcome.

Mean and standard deviations of anticipated TBR in ACS population at 30 days:

- Aorta MDS: 3.3 ± 0.6
- Carotid artery MDS: 2.6 ± 0.4

Table 5: Power calculations using a 1-sided p-value of 0.05 and assuming a normal distribution.

	N in each group	Mean (SD) TBR in ACS Population at 30 days	Estimated Power at 10% & 15% TBR Difference	Detectable Point Estimate at 70% & 80% Power
Aorta MDS	N = 30	3.3 (0.6)	69% 94%	-10.3% -11.8%
Carotid MDS	N = 30	2.6 (0.4)	81% 98%	-8.7% -10.0%

d. Early stopping rules.

The Johns Hopkins DSMB will perform any interim analysis they require to monitor patient safety and provide reports advising continuation of the study.

8. Risks

a. Medical risks, listing all procedures, their major and minor risks and expected frequency.

Study drug:

Evolocumab is supplied as a sterile, single-use, preservative free solution for subcutaneous injection in a disposable, spring-based prefilled autoinjector/pen (AI/pen). The AI/pen contains a 1.0 mL deliverable volume of 140 mg/mL evolocumab or placebo and three 140mg/ml AI/pens will be dispensed by the Johns Hopkins Investigational Drug Service and will be administered by one of the investigators to each study participant. Evolocumab is well tolerated with few side effects. A prior clinical trial reported no significant differences in adverse events (AEs) and serious adverse events (SAEs) between those participants receiving evolocumab and

those receiving placebo in a randomized, placebo- controlled trial over three months of administration (Rutherford 2) [47]. Other trials reported no SAEs and no differences in AEs between treatment with the PCSK9 inhibitor and placebo[48]. The most common reasons for withdrawal were unrelated to the study drug. The GAUSS-3 randomized trial comparing evolocumab and ezetimibe reported no difference in AEs between the study arms and no SAEs reported over 24 weeks [49]. A recent large metanalysis of PCSK9 inhibitor trials showed no difference in treatment-emergent AEs or SAEs in evolocumab-treated and placebo-administered patients[50]. Overall, injection site reactions are manageable and rarely lead to discontinuation of the PCSK9 antibody. Other side effects are all comparable to those reported in the placebo groups. Importantly, very few musculoskeletal side effects are reported in major clinical trials, and are comparable to those seen in placebo-treated patients, and there is no difference in laboratory abnormalities reflective of liver or kidney damage over 12 weeks of treatment in the evolocumab vs. placebo groups. [50]

Table 6: The most common adverse effects of evolocumab are listed below and do not differ from those which occurred in patients who received placebo. [50]

Most Common Safety Endpoints	Evolocumab (12 week)	Placebo (12 week)	P value
	Pooled event rate (95% CI)		
Musculoskeletal disorders	9.8 (4.1-15.4)	7.1 (1.6-12.6)	0.74
Nasopharyngitis	6.2 (3.6-8.8)	4.2 (2.1-6.3)	0.11
Gastrointestinal disorders	5.6 (2.7-8.4)	5.3 (1.9-8.7)	0.73
Upper respiratory tract infection	4.2 (2.5-5.9)	2.9 (0.3-5.6)	0.96
Headache	3.4 (2.2-4.6)	2.6 (1.5-3.7)	0.33
Injection site reactions	2.2 (1.3-3.1)	1.7 (0.9-2.5)	0.82

PET studies:

Intravenous Line during PET study: can cause some slight discomfort when the needle is inserted into the arm vein. The potential side effects of taking blood samples may include dizziness, soreness and/or bruising of the skin for several days. In very rare circumstances, bleeding or infection can develop at the needle puncture site. However, because the procedure is performed by a trained specialist using sterile and standard medical practices, that is very unlikely.

Isotope (F-18 fluorodeoxyglucose (FDG) Injections (PET-scans):

This research study includes exposure to radiation from x-rays or gamma rays. This radiation exposure is for research purposes only and is not part of medical care. X-rays and gamma rays from natural or medical sources can damage the genetic material (DNA) in cells. At low doses, the body is usually able to repair the damage.

The radiation exposure that a study participant will get in this research study is 3.1 rem. This is more than the 0.3 rem that the average person in the United States gets each year from natural sources like the sun, outer space, air, food and soil. It is less than the 5 rems of radiation that is allowed each year for people who are exposed to radiation in their jobs.

The radiation exposure described here is what the study participant will get from this research study only. It does not include any exposure the patient may have received or will receive from other tests outside of this study that are a part of medical care. Radiation risk builds up with each exposure. The study participant should think about his history of radiation exposure from

tests (like x-rays or CT scans) in deciding about the radiation in this study. We encourage all study participants to ask questions about the total amount of radiation he/she will be receiving.

b. Steps taken to minimize the risks.

To protect against and minimize the potential risks of evolocumab treatment, study participants will undergo a careful history as well as physical examinations at baseline to identify any condition which might increase their risk from the medication but not known to the patients or documented in their medical records. The subcutaneous injections of the study drug (evolocumab or placebo) will be administered by one of the physician investigators. In addition, patients will be evaluated closely at regular intervals following the injection for side-effects. Patients who experience significant symptoms will be evaluated.

Trained personnel will perform the blood collection procedure and will make every effort to minimize any risks or discomfort.

c. Plan for reporting unanticipated problems or study deviations.

All clinically significant unanticipated problems or study deviations will be reported to the DSMB and the IRB according to The Johns Hopkins Medicine Institutional Review Boards published guidelines. The DSMB will include a cardiologist familiar with the management of patients with acute coronary symptoms, a statistician and an individual with a background in medical ethics. The DSMB will have access to study drug assignment and will make recommendations to [name] regarding any safety concerns and continuation of the study.

d. Legal risks such as the risks that would be associated with breach of confidentiality.

Once the data are acquired, they will be assigned a code for each subject with identification secured and accessible only to the principal and other investigators, and the research coordinator. Patient clinical information such as copies of clinical studies and imaging reports will be filed in a locked filing cabinet with access under control of [name] or one of the other investigators and study coordinators. Patient information summarized and/or converted into electronic form (tables, images, etc.) will be identified by the assigned code. We will abide by the Johns Hopkins Institutional policy that all identifiers in images and data acquired under IRB-approved research protocols must be removed if they leave the institution, for example in presentations.

e. Financial risks to the participants.

All study related costs will be paid from research sources, as stated in the consent form.

9. Benefits

a. Description of the probable benefits for the participant and for society.

Results from this study may benefit patients with an ACS in the future by providing information on the role of lipid lowering and anti-inflammatory medications in patients with an ACS. This would support the use of PCSK9 inhibitors to complement existing ACS treatment strategies in this population. However, we do not currently know whether subjects

will have an immediate benefit. It could be that this agent (evolocumab) reduces inflammation and LDL cholesterol and improves vascular and/or myocardial inflammation and this would, at least in the short term, benefit the patients receiving that drug. In prior non-ACS studies, the risks of receiving evolocumab were not different from placebo. In addition, the risks would be relatively short term since study participants will be only receiving a one-time dose of evolocumab. The low risk is reasonable in relation to the potential knowledge gained that may guide future therapeutic studies.

10. Payment and Remuneration

- a. Detail compensation for participants including possible total compensation, proposed bonus, and any proposed reductions or penalties for not completing the protocol.

For every outpatient visit study participants will receive \$75. For study participants who have to travel \geq 75 miles, or have an early morning heart scan, a hotel room for one night may be provided. Additionally, study participants will be reimbursed for transportation and parking expenses and given a \$10 meal voucher following procedures requiring prior fasting.

11. Costs

- a. Detail costs of study procedure(s) or drug (s) or substance(s) to participants and identify who will pay for them.

There is no cost to the participants related to the study procedures or drugs.

REFERENCES:

1. Ferrante, G., et al., *High levels of systemic myeloperoxidase are associated with coronary plaque erosion in patients with acute coronary syndromes: a clinicopathological study*. Circulation, 2010. **122**(24): p. 2505-13.
2. Mannsverk, J., et al., *Trends in Modifiable Risk Factors Are Associated With Declining Incidence of Hospitalized and Nonhospitalized Acute Coronary Heart Disease in a Population*. Circulation, 2016. **133**(1): p. 74-81.
3. Khera, S., et al., *Non-ST-elevation myocardial infarction in the United States: contemporary trends in incidence, utilization of the early invasive strategy, and in-hospital outcomes*. J Am Heart Assoc, 2014. **3**(4).

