This is a phase 2, double-blind, randomized, placebo controlled clinical trial of 420 mg evolocumab administered subcutaneously using an autoinjector/pen in NSTEMI patients during early hospitalization at the Johns Hopkins Hospital or the Johns Hopkins Bayview Medical Center.. The placebo and evolocumab will be given exactly the same way with the same Amgen provided device. All participants will receive standard care for NSTEMI, including high dose statin, aspirin, beta blocker, and, as appropriate, ACE-I or ARB and early intervention. High dose statin therapy consists of atorvastatin 40mg or 80mg or rosuvastatin 20mg or 40mg per the most recent ACC/AHA guidelines. [43] After signing informed consent, subjects will be randomized to receive one dose of evolocumab or matching placebo subcutaneously. Research blood samples for LDL-C and inflammatory markers, and PET imaging assessment of vascular inflammation as well as echocardiographic studies for left ventricular function will be obtained. An independent Data and Safety Monitoring Committee will review all potential side effects and clinical outcomes during the twelve months of follow-up.

At the 30-day follow-up visit we will perform a physical exam and obtain a history of any clinical events including adverse events. We will perform a second FDG-PET study to assess vascular and myocardial; inflammation. Additionally, we will assess LDL-C and serum markers of inflammation and endothelial function as outlined in 2.2 a.

At the 6-month follow-up visit will perform a physical exam and obtain a history of any clinical events including adverse events. Additionally, we will assess LDL-C and serum markers of inflammation and endothelial function as outlined in 2.2 a.

At the 9-month follow-up visit, we will contact the participant by phone to learn of any adverse events. If the participant was admitted to the Emergency Department or Hospital we will obtain permission to obtain medical records.

At 12-month follow-up visit we will assess lipid profile and serum markers of inflammation and endothelial function as outlined in 2.2 a.

All above are research studies with the exception of the clinical echocardiogram during the initial hospitalization.

b. Study duration and number of study visits required of research participants.

The study duration for each participant is twelve-months and there are three study visits required.

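### Exclusion item g checks contraception only backward over one month; the available protocol text shows no pregnancy or breastfeeding exclusion, no pregnancy test and no contraception rule after dosing

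*Combined protocol and SAP*

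**What the plan says.** Section 5.1 admits patients on the criterion "Age 25 to 90 years", so women of reproductive age are in range. Section 5.2, item g, excludes women of childbearing potential and defines them as follows: "This is a female subject who has not used acceptable method(s) of birth control (see below) for at least one month prior to screening", with the exemption "unless the subject is sterilized or postmenopausal". The accepted methods are described as having a failure rate below 1% per year when used properly. The list ends with "Sexual abstinence".

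Section 6.b states that evolocumab is given outside its approved indication. Section 4.a classes all the procedures it lists as research except the initial clinical echocardiogram, and for the 30-day visit it says: "We will perform a second FDG-PET study to assess vascular and myocardial; inflammation". The first scan takes place early in the hospital stay or shortly after discharge (Section 2.2.b). Section 8.a gives the dose: "The radiation exposure that a study participant will get in this research study is 3.1 rem".

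Section 4.f limits removal from the study to participants who unexpectedly go to CABG. The lettered exclusions in Section 5.2 run from a to e and then resume at g.

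**The concern.** A criterion on childbearing potential is normally there to prevent exposure of a fetus. Item g tests something else, namely what a woman did in the month before screening. It does not establish whether she is pregnant now, and it places no obligation on her after screening, although the dose and both PET scans come later. The drug is used off-label and the radiation is not part of her care, so an exposed pregnancy would be a consequence of taking part in the study. The stake is participant safety. LDL-C, TBR and the power tables are not touched.

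**Working it through.** The plan gives no figure to reproduce here. The check is to read item g as a logical rule, apply it case by case, and then look for any other safeguard.

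**The rule.** Let M = a listed method used for at least one month before screening, S = sterilized, P = postmenopausal as defined. A woman is excluded if NOT (M or S or P).

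**Cases, none of them sterilized or postmenopausal:**

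1. Pregnant, no listed method in the past month. M is false: excluded.
2. Pregnant from a conception before the look-back month, and since then abstinent or using a listed method. M is true: not excluded.
3. Pregnant because a listed method failed. M is true: not excluded.
4. Breastfeeding and using a listed method such as an IUD. M is true: not excluded.
5. Not pregnant at screening, stops contraception after the injection. M was true at screening and nothing later applies: she remains in the study and is due for the 30-day scan.

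**Size of case 3.** The protocol's ceiling for an accepted method is 1% per year. The one-month failure probability is 1 − (1 − 0.01)^(1/12) = 0.00084, or about 0.08%. As a deliberately extreme bound, suppose all 60 participants (30 per group, Section 7.c) were women relying on such a method. The chance of at least one failure in one month would be 1 − (1 − 0.01)^(60/12) = 1 − 0.99^5 = 0.049, or about 5%. The real figure is much lower, because only a fraction of participants will be such women. A longer undetected interval would raise it roughly in proportion. Both figures assume consistent and correct use, as the protocol's own ceiling does.

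**Size of cases 2, 4 and 5.** The documents give no breakdown of expected participants by sex or age, so these cannot be calculated. My assumption is zero or one pregnant woman among those screened for 60 places, and only some of these would pass item g.

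**Other safeguards in the text:**

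- Section 2.2.a (blood markers) lists no pregnancy test.
- Section 4.a (procedures) has none before the dose or either scan.
- Section 4.f (removal) does not cover a pregnancy found after the dose. Read literally, such a woman is not removed, and no section says what happens to her second scan.
- Section 5.2, item h, excludes a contraindication to statins, but does not list the contraindications.
- Section 5.1.c requires the attending physician's permission, and Section 8.b provides a baseline history and examination. Neither mentions pregnancy.
- Section 8.a does not mention fetal risk.

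**The case against.** The strongest reply is that item g already does most of the work. A pregnant woman who was not using contraception, the most obvious case, is excluded. A reader might infer that any pregnant woman screened would be enrolled; case 1 shows that this is untrue. The opening is confined to cases 2 to 5.

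Second, a reader might infer that the protocol never excludes pregnancy. That cannot be established. Item f is absent from the list; it may have been deleted or lost when the PDF was read. The consent pages are not available either and could carry a warning. This stands as a limit on the claim. It does not answer the whole point: even if item f excluded pregnancy, the procedures still show no test and no forward contraception rule, and consent wording does not replace a criterion or a scheduled test.

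Third, the statin exclusion, the physician's permission and the baseline examination could catch a known pregnancy. They may, but as written none can be relied on to detect an early, unrecognized one.

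Fourth, the 3.1 rem might be taken as the fetal exposure. It is the participant's total research dose. No fetal dose is given, and a woman who conceived after the first scan would face only the second.

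Finally, a reader might go on to call the menopause definition wrong because it requires age 55 or over as well as "12 months of spontaneous and continuous amenorrhea in a female" of that age. The documents do not support this. The age floor is a conservative choice that nothing else in them contradicts. Women under 55 can still enter if they are sterilized or use any listed method, abstinence included. No figure in the documents shows how many would be turned away.

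**Conclusion.** The point holds in a limited form. As written, item g is a one-month retrospective contraception check. It can admit a pregnant woman by a narrow route, it can admit a breastfeeding woman, and it lapses at screening, before the dose and both scans. Few cases are expected, and there is no effect on sample size, power or analysis. It is still worth correcting, because the possible harm is serious, avoidable and arises from research procedures. The conclusion rests on two assumptions: that the missing item f did not deal with pregnancy, and that no testing or contraception instruction exists in a document not available here. If item f did exclude pregnancy, what remains is the absence of a test and of a forward contraception requirement.

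**What to change.** First, the sponsor should state what item f said. Then amend item g in three respects:

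- Name pregnancy and breastfeeding as exclusions.
- Require a negative pregnancy test in women of childbearing potential before dosing and again before each research PET scan.
- Make the contraception requirement run forward from screening through the 30-day scan.

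Section 4.f should be reconciled with the amended item, since it now allows removal only for CABG. How a pregnancy found after dosing is handled is for the sponsor to specify.

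The cost is one eligibility amendment and a small number of tests. Blood is already collected at baseline and at 30 days (Section 2.2.a), so those tests need little or no extra sampling, provided the result is back before the injection or scan. The small downside is waiting for that result in a few women.

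### Section 7.b sets a one-sided p ≤ 0.05 rule but names the Kruskal-Wallis test for 30-day TBR; its two-group p-value has no direction and, read at 0.05, has Table 4's power rather than Table 3's

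*Combined protocol and SAP*

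**What the plan says.** Section 7.b plans two analyses of TBR. Percent change from the early scan is compared by ANCOVA with baseline TBR as covariate. The 30-day between-group difference in the index-vessel most diseased segment (MDS) "at 30 days will be analyzed using Kruskal Walis testing". The section closes with its significance rule: "A one-sided p-value ≤ 0.05 will be considered significant, based on the assumption that evolocumab will reduce, and not increase, inflammation".

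Section 7.c gives TBR power for 30 patients per arm. Table 3 comes first and is one-sided; its caption says that it "only assumes that PCSK9 inhibition will lower TBR in the most diseased segment (MDS) and will not raise TBR". The two-sided table is presented as an extra: "For completeness, we replicated the analysis in Table 4 using a 2-sided p-value of 0.05". Section 7.c says these calculations use non-parametric statistics. It lists anticipated 30-day values of 3.3 ± 0.6 (aorta) and 2.6 ± 0.4 (carotid).

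**The concern.** A one-sided rule needs a test statistic with a sign. The ANCOVA contrast has one. The Kruskal-Wallis statistic does not, and 7.b gives no way to get from its p-value to a one-sided one.

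An analyst who runs the named test and compares the printed p-value with 0.05 is doing a two-sided test. A result with lower TBR on evolocumab and a Kruskal-Wallis p between 0.05 and 0.10 is then called non-significant, although it meets the stated one-sided rule. A result with higher TBR on evolocumab and p ≤ 0.05 is called significant, although the rule excludes it. Halving the p-value without checking direction is also wrong: it rejects about 10% of the time when there is no effect. The conversion should be written down before unblinding.

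**Working it through.** **Inputs (section 7.c).** n = 30 per arm; control mean and SD 3.3 and 0.6 (aorta), 2.6 and 0.4 (carotid); differences of 10% and 15%. Assumption: normal data with a shift in location.

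**1. What the named test reports.** Let W be the rank sum in the evolocumab arm, with 60 patients in all. Under no effect W has mean 30 × 61/2 = 915 and variance 30 × 30 × 61/12 = 4,575, so z = (W − 915)/67.64. With two groups, the Kruskal-Wallis statistic is H = z², and its p-value is P(χ² on 1 df ≥ z²) = 2Φ(−|z|). That is the two-sided rank-sum p-value without continuity correction. In one simulated data set, Kruskal-Wallis gave 0.00779 whichever arm was entered first, as did the two-sided rank-sum test. The one-sided rank-sum p-values were 0.0039 (evolocumab lower) and 0.9961 (evolocumab higher).

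The two readings are therefore:
- Kruskal-Wallis p ≤ 0.05: |z| ≥ 1.960, in either direction.
- One-sided rank-sum p ≤ 0.05: z ≤ −1.645, which is the same as Kruskal-Wallis p ≤ 0.10 with evolocumab lower.

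**2. Reproducing the plan's tables.** Approximate rank-test power is Φ(δ / [SD × √(2/(30 × 0.955))] − c), where 0.955 is the normal-theory efficiency of the rank-sum test (an assumption) and c is 1.645 or 1.960. For the aorta at 10%, δ = 0.33 and the standard error is 0.6 × √(2/28.65) = 0.1585, so δ/SE = 2.082. One-sided power is Φ(0.437) = 66.9% (Table 3: 66%). Two-sided power is Φ(0.122) = 54.8% (Table 4: 54%). The other cells of both tables reproduce within 2 points.

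**3. Simulating the two readings** (200,000 trials per cell):

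| | Difference | Kruskal-Wallis p ≤ 0.05 | Table 4 | One-sided rank-sum p ≤ 0.05 | Table 3 | Readings disagree |
|---|---|---|---|---|---|---|
| Aorta | 10% | 53.2% | 54% | 65.9% | 66% | 12.6% |
| Aorta | 15% | 86.5% | 87% | 92.3% | 93% | 5.8% |
| Carotid | 10% | 67.5% | 68% | 78.1% | 78% | 10.6% |
| Carotid | 15% | 95.1% | 95% | 97.6% | 98% | 2.5% |

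At a true 5% difference, the low end of the 5%-15% range quoted in 7.c, the readings disagree in 9.5% (aorta) and 10.7% (carotid) of trials.

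**4. No effect.** Kruskal-Wallis at 0.05 rejects in about 5% of trials, about 2.5% in each direction. The one-sided test rejects in about 5%, all with evolocumab lower. The readings disagree in about 5%: roughly 2.5% significant only one-sided, in the drug's favour, and 2.5% significant only by Kruskal-Wallis, against it.

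**5. Dependence on the SD.** Tables 3 and 4 print IQRs of 2.7-4.0 and 2.1-3.0. Under normality these imply SDs of 1.3/1.349 = 0.96 and 0.9/1.349 = 0.67, larger than the listed 0.6 and 0.4. At those SDs, one-sided rank-sum power at a 10% difference is only about 35% (aorta) and 42% (carotid). Table 3 therefore holds under the listed SDs only.

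**The case against.** The best reply is that nothing is undecided. The rule closing 7.b says one-sided, Table 3 leads, and Table 4 is offered only as a supplement. A competent analyst can apply the rule by checking which arm is lower and using Kruskal-Wallis p ≤ 0.10. Two-sided power is also printed openly in Table 4, so no reader is misled about what a two-sided test would achieve. Most of this stands. It would be too strong to say that the named test cannot serve the rule, or that the intended sidedness is unknown. What remains is that 7.b names a test whose printed p-value does not follow the rule, and gives no conversion.

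A reader might also infer that one-sided testing of the primary LDL-C endpoint is an error, because the only stated reason concerns inflammation while 7.c reports LDL-C power "using a one-sided p-value of 0.05, the study has nearly 100% power to detect this difference". The documents do not support that:
- Section 7.a names a model but no level, and the one-sided rule sits under secondary outcomes. One-sided testing of LDL-C is thus inferred from a power statement.
- The Abstract hypothesises a decrease in LDL-C, so a direction is stated, though not offered as the reason.
- The choice hardly matters at the anticipated difference of 55 − 28 = 27 mg/dL. Even at the larger SD of 21.5 implied by the 30-day IQRs, power is 99.9% one-sided and 99.8% two-sided.
- A two-sided replacement for the 9.5 mg/dL detectable difference cannot be fixed from the documents. It runs from about 7.7 (Table 2's SDs) to 15.8 mg/dL (IQR-based SD).

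The sentence "Table 1 uses a 1-sided p-value of 0.05, under the hypothesis that evolocumab will lower inflammation and will not raise it" might seem to attach the inflammation reason to the LDL-C table. It stands in the TBR paragraph and describes Table 3, so it reads as a numbering slip.

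**Conclusion.** The test named for 30-day TBR does not match the decision rule or the lead power table. Read as reported, it costs about 13 points of power for the aorta and 11 for the carotid at a 10% difference, and it puts half of its 5% error in the direction the rule excludes. The mismatch affects the conclusion only when the p-value falls in the disputed zone: about 11% to 13% of trials at a true 10% difference and about 5% under no effect. These figures assume 30 evaluable patients per arm, normal data and SDs of 0.6 and 0.4.

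This is a correctable mismatch in one secondary analysis. It does not show that the sidedness of the TBR comparison was left open, and it gives no ground for requiring two-sided testing of LDL-C.

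**What to change.** In 7.b, replace the Kruskal-Wallis sentence with a one-sided Wilcoxon rank-sum test of 30-day index-vessel MDS TBR (alternative: lower TBR on evolocumab; alpha 0.05). If the Kruskal-Wallis name is to stay, state the equivalent rule: p ≤ 0.10 with TBR lower on evolocumab.

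In 7.c, say that Table 3 is the power table for this test under SDs of 0.6 and 0.4, and note that the table's own IQRs imply larger SDs under normality and lower power. Correct the reference to Table 1 in the TBR paragraph to Table 3.

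These are wording changes only, with no change in sample size. The 5% chance of a false claim for the drug on this endpoint is what the plan's one-sided rule already accepts, and the power is what Table 3 already states.
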